The primary outcome of the trial will be the pathologic changes that result from bronchoscopic laser ablation of peripheral lung tumors, and will be categorized into three groups: 1. Complete Ablation: absence of staining (MAB 1273 or NADH, or both) of tumor cells. 2. Quasi-Complete Ablation: positive staining of $\leq 10\%$ of tumor cells. 3. Incomplete ablation: positive staining in $> 10\%$ of tumor cells. The secondary outcomes include the safety of this ablative procedure which will be measured by serious adverse effects (SAE), defined as pneumothorax requiring chest tube, bleeding requiring balloon tamponade or leading to respiratory failure, and hypoxemia ($\text{SpaO}_2 < 90\%$ for > 1 min) during bronchoscopy, post-bronchoscopy pneumonitis with need of supplemental oxygen., as well as pathologic changes observed in the lung tissue surrounding the treated lung tumor, and radiographic changes observed by cone-beam CT immediately after the application of bronchoscopic laser ablation.

Only patients who undergo bronchoscopic tumor ablation will be included in the analysis.

We will conduct extensive descriptive analyses of the data collected. We will calculate the appropriate summary statistics and 90% confidence intervals (CIs) for the measures of interest described in primary and secondary objectives. For example, we will obtain frequencies and proportions of the three tumor ablation outcome categories (complete, quasi-complete, and incomplete) for the primary objective, and record the number of each type of SAE at each level of laser power. Our goal is to simply assess the magnitude and obtain preliminary estimates of this technique to proceed to our next project which is the development of a large multicenter randomized trial comparing the effectiveness of this new bronchoscopic laser ablative technique vs. the standard of care for these patients, SBRT, in patients with medically inoperable early lung cancer.

[figure not shown]
Sample Size Justification. This is a pilot trial to assess whether a new technique can be delivered safely to humans and provide complete ablation of lung tumors, and is not powered for significance in statistical comparison as there is insufficient existing evidence to predict the likely outcomes. A total of 15 patients will be recruited from UT MD Anderson Cancer Center. With this sample size, the 90% confidence interval for an expected 70% of complete ablation rate can be estimated with a maximum width of 0.195. This power was based on nQuery Advisor.

Toxicity Monitoring

[figure not shown]
We will monitor patients for unacceptable toxicity in cohorts of size 5 [11]. An unacceptable toxicity in this study is defined as pneumothorax requiring chest tube, bleeding requiring balloon tamponade or leading to respiratory failure, and hypoxemia ($\text{SpaO}_2 < 90\%$ for > 1 min) during bronchoscopy, post-bronchoscopy pneumonitis with need of supplemental oxygen.

If we find $\text{Pr}[\pi_T > 0.3 | \text{data}] > 0.85$, where π_T is the true proportion of patients who experience unacceptable toxicities and follows a $\text{beta}(0.6, 1.4)$ distribution, we will stop the trial for toxicity.

The stopping boundaries for toxicity are found in Table 1. Table 2 shows the operating characteristics for this design. The stopping boundaries and operating characteristics were created based upon 1,000 simulations using Multc Lean Desktop V2.1.

Other Considerations

REFERENCES

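### Does the primary outcome need a written rule for a tumor whose MAB 1273 and NADH stains disagree?

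*Combined protocol and SAP*

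**What the plan says.** Under Statistical Considerations and Sample Size Justification, the primary outcome "will be categorized into three groups". Complete ablation is "absence of staining (MAB 1273 or NADH, or both) of tumor cells". The second category opens "Quasi-Complete Ablation: positive staining of" and has a ceiling of 10% of tumor cells. The third opens "Incomplete ablation: positive staining in" and takes everything above 10%. Neither of these two names a stain.

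The planned analysis is descriptive: "we will obtain frequencies and proportions of the three tumor ablation outcome categories", with 90% confidence intervals. The purpose is to "obtain preliminary estimates of this technique to proceed to our next project", a randomized comparison with SBRT. The Sample Size Justification takes 15 patients and "an expected 70% of complete ablation rate", and says that the pilot is not powered for statistical comparisons.

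The printed text does not say when one stain or both are run, how two readings combine, or which category takes precedence.

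**The concern.** Frequencies and proportions over three groups require one category per tumor. The words on complete ablation allow two stains to be read, and two stains can disagree.

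- If one negative stain is enough for complete, a 0%/20% tumor meets both the complete and the incomplete wording.
- If both stains must be negative for complete, but the other two categories are judged stain by stain, a 5%/30% tumor is quasi-complete on one stain and incomplete on the other.
- If only one stain is read per tumor, nothing overlaps, but the category can depend on which stain was used.

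This is the only primary outcome, and the sample size is justified on the complete rate. Without a rule fixed in advance, a discordant tumor could be assigned after its stains are seen, and an optimistic complete rate could be carried into the planning of the next trial.

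**Working it through.** **Inputs.** From the Sample Size Justification: n = 15, expected complete rate 0.70, stated precision 0.195. From Statistical Considerations: 90% confidence level (z = 1.645). The documents give no discordance or staining error rate, so those below are assumptions.

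**The plan's own figure.** 1.645 × √(0.70 × 0.30 / 15) = 0.195. The stated precision is reproduced as a half-width (full width 0.389). It does not depend on how the stains are combined.

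**Does the wording force an overlap?** Take readings of 0%, 5% and 30% on each stain. If a cell counts as positive when either stain marks it, the positive share lies between the larger reading and the sum of the two.

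| Two readings | Judged stain by stain | Cell positive if either stain marks it |
|---|---|---|
| 0% / 0% | complete | complete |
| 0% / 5% | complete and quasi-complete | quasi-complete (5%) |
| 0% / 30% | complete and incomplete | incomplete (30%) |
| 5% / 5% | quasi-complete | quasi-complete (5% to 10%) |
| 5% / 30% | quasi-complete and incomplete | incomplete (30% to 35%) |
| 30% / 30% | incomplete | incomplete (at least 30%) |

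The overlap arises only when the stains are judged separately. The right-hand reading is not printed, but it fits a definition expressed in tumor cells: absence of staining by one stain, the other or both can be read as no mark from either. Some pairs, such as 8%/8% (8% to 16%), would need a look at the cells themselves or use of the larger percentage.

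**Size per tumor.** One discordant tumor moves a proportion by 1/15 = 6.7 points. For example, 10/15 = 66.7% (exact 90% CI 42.3% to 85.8%) becomes 11/15 = 73.3% (48.9% to 90.3%).

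**Missed residual tumor.** Assume a true complete rate of 0.70, that each stain independently misses residual cells with probability q, and no false positives. The complete rate is then 0.7 + 0.3q² if both stains must be negative, 0.7 + 0.3q on one stain, and 0.7 + 0.3[1 − (1 − q)²] if either negative suffices.

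| q | Both negative | One stain | Either negative | Either minus both |
|---|---|---|---|---|
| 0 | 70.0% | 70.0% | 70.0% | 0 |
| 0.05 | 70.1% | 71.5% | 72.9% | 2.9 points |
| 0.10 | 70.3% | 73.0% | 75.7% | 5.4 points |
| 0.20 | 71.2% | 76.0% | 80.8% | 9.6 points |

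The direction is fixed. Any tumor negative on both stains is also negative on one, so single-stain or either-negative classification can only equal or exceed the both-negative rate. Positively correlated misses narrow the spread.

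**False positives.** Now assume no misses and an independent false-positive probability f per stain. Classifying on the higher percentage gives a complete rate of 0.7(1 − f)², and one named stain gives 0.7(1 − f).

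| f | Higher percentage | One named stain |
|---|---|---|
| 0.02 | 67.2% | 68.6% |
| 0.05 | 63.2% | 66.5% |
| 0.10 | 56.7% | 63.0% |

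At f = 0.10 the strict rule loses 70.0 − 56.7 = 13.3 points. That exceeds the 5.4-point gap between the either-negative and both-negative rules at q = 0.10.

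**The case for a change.** The strongest case for a change is that the gap sits in the sole primary outcome, that the wording itself allows two stains, and that one sentence written before tissue is read would close it at almost no cost. In a sample of 15, three discordant tumors would move a proportion by 3/15 = 20.0 points, more than the 19.5-point half-width. The arithmetic is right, and the printed text does lack a combination rule.

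Three things limit what follows from this. First, the public copy has a heading for design and procedure but no procedure. It also plans to "record the number of each type of SAE at each level of laser power" although laser power levels are defined nowhere, so procedural text is evidently lost and pathology methods may have gone with it. An absence in such a copy does not show an absence in the plan. Second, the conflict needs both stains read on the same tumor, which no section says is routine. Third, the remedy is not neutral. A higher-percentage rule lowers the complete rate if a stain gives false positives, and a single named stain works only if that stain was run on every tumor. The documents give neither error rate, so they do not favor one rule over another.

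What stands is a fair question to the investigators: how are the two stains combined?

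**Conclusion.** No change follows. The printed definition does not by itself assign a tumor with discordant stains to one category, but this is a gap of detail that the pathologists would fill sensibly, in a copy that may have lost the relevant section. At least one natural reading gives three exclusive groups.

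Each discordant tumor is worth 6.7 points. Under the assumed independent miss rates up to 0.20, the choice of rule moves the complete rate by 0 to 9.6 points, within the 19.5-point half-width. The actual discordance rate is unknown and may be zero. Relative to requiring both stains negative, the looser readings can only raise the complete rate or leave it unchanged, which is worth remembering when the estimate is used for planning. The printed text has no efficacy test, and the rule under Toxicity Monitoring does not use this outcome, so no decision within the trial turns on the point.

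### The stated precision of 0.195 for the 90% CI at n = 15 is a Wald half-width, not a maximum width; the full width is about 0.39, and no small-sample interval method is named

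*Combined protocol and SAP*

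**What the plan says.** The section on statistical considerations and sample size describes a descriptive analysis and commits to intervals in general terms: "We will calculate the appropriate summary statistics and 90% confidence intervals (CIs) for the measures of interest described in primary and secondary objectives". The measures concerned include the three ablation categories (primary) and safety, measured by serious adverse effects (secondary). Only patients who undergo ablation are analysed, so the denominator is at most 15.

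The sample size paragraph in the same section gives the one quantified interval. "A total of 15 patients will be recruited from UT MD Anderson Cancer Center", and with that number "the 90% confidence interval for an expected 70% of complete ablation rate can be estimated with a maximum width of 0.195". The source is given as software only: "This power was based on nQuery Advisor". Neither place names an interval formula or says how a count of 0 or 15 out of 15 would be handled.

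**The concern.** A full width of 0.195 around 70% would mean an interval of roughly 0.60 to 0.80. That is implausibly tight for 15 patients, and it is the only justification offered for the sample size. If the figure is really a half-width, readers are told that the trial is twice as precise as it is.

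The figure also hints at a normal-approximation method. In 15 patients, with proportions that may lie near 0 or 1, that method can fall well short of its nominal level. The estimates are meant to feed the planning of a multicenter randomized trial, so their uncertainty should be stated correctly.

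**Working it through.** **Inputs.** From the sample size paragraph: n = 15, confidence level 90%, expected complete ablation rate 0.70, stated precision 0.195. Assumption: the interval is two-sided, so z = 1.645.

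**1. Reproducing 0.195.**
- Wald half-width = z × √(p(1 − p)/n) = 1.645 × √(0.7 × 0.3/15) = 1.645 × 0.1183 = 0.1946, which rounds to 0.195.
- Full width = 2 × 0.1946 = 0.389, that is, 0.505 to 0.895.
- Reverse check: a half-width of 0.195 needs n = (1.645/0.195)² × 0.21 = 14.94, so 15. A full width of 0.195 would need n = (1.645/0.0975)² × 0.21, which rounds up to 60.
- Other methods at 70% and n = 15 give different half-widths: Wilson 0.182, Agresti-Coull 0.184, Jeffreys 0.185, Clopper-Pearson 0.213 (interpolated at 10.5 events), Wald with continuity correction 0.228. Of the methods tried, only plain Wald gives 0.195.

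**2. Is it a maximum?** At p = 0.5 the Wald half-width is 1.645 × √(0.25/15) = 0.212 and the full width is 0.425. So 0.195 is not a maximum over rates, either as a half-width or as a full width.

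**3. Coverage.** For each true rate p, add the Binomial(15, p) probabilities of the outcomes whose interval contains p. At p = 0.70 the Wald interval contains 0.70 only for 8 to 12 events: 0.0811 + 0.1472 + 0.2061 + 0.2186 + 0.1700 = 0.823. The Wilson interval also contains it at 13 events: 0.823 + 0.0916 = 0.915.

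| True rate | Wald | Wilson | Clopper-Pearson |
|---|---|---|---|
| 0.50 | 88.2% | 88.2% | 96.5% |
| 0.65 | 89.6% | 89.6% | 94.4% |
| 0.70 | 82.3% | 91.5% | 94.9% |
| 0.80 | 81.5% | 90.4% | 94.7% |
| 0.90 | 78.1% | 94.4% | 98.7% |
| Mean over 0.60–0.80 | 85.7% | 90.2% | 94.6% |

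**4. Extreme counts.**

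| Count | Wald | Wilson | Clopper-Pearson |
|---|---|---|---|
| 0/15 | 0 to 0 | 0 to 0.153 | 0 to 0.181 |
| 14/15 | 0.827 to 1.039 | 0.749 to 0.985 | 0.721 to 0.997 |
| 15/15 | 1 to 1 | 0.847 to 1 | 0.819 to 1 |

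The Clopper-Pearson limit at 0/15 is 1 − 0.05^(1/15) = 0.181. The documents give no expected SAE rate. On assumed rates, zero events in 15 has probability 0.95^15 = 46% at 5%, 0.90^15 = 21% at 10% and 0.70^15 = 0.5% at 30%.

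**5. Width on a small-sample basis.** Weighting each outcome's width by its Binomial(15, 0.70) probability gives an expected full width of 0.412 for Clopper-Pearson (largest over all outcomes 0.456) and 0.351 for Wilson (largest 0.390).

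**The case against.** The strongest reply is that the plan never says it will report Wald intervals. It promises appropriate intervals, and a normal-approximation formula used for planning does not fix the method used for reporting. This stands. A reader might infer that the trial will publish a safety interval of 0 to 0, or an ablation interval running above 1. The documents do not support that; these are risks left open by an unnamed method.

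It is also fair to say that 82% is not the coverage of Wald at n = 15 in general. Coverage moves up and down with the true rate and is close to nominal at 65%. Nor is Wilson uniformly at or above 90%: it equals Wald at 50% and 65%, and its minimum over 0.60 to 0.80 is 85.6%. Clopper-Pearson never falls below 90% but is conservative. The choice between the two is partly one of preference.

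A reader might further infer that these intervals are the trial's entire inference. They are not. Toxicity is monitored by a separate Bayesian rule with a beta prior, applied in cohorts of five, which does not depend on the interval method. At the 30% reference rate in that rule, 0/15 is very unlikely, so the zero-event case matters only if the true SAE rate is well below it.

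Finally, this is a descriptive pilot, and readers can compute their own intervals from reported counts. That limits the harm. It does not rescue the printed precision figure, which is wrong under any of the methods tried.

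**Conclusion.** The precision sentence is in error. The stated 0.195 is the Wald half-width at 70%; the full width is 0.389, twice the printed value, and 0.195 is not a maximum. This rests only on the plan's own n, rate and confidence level and on a two-sided interval.

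The method behind the figure is a poor basis at this sample size: 82.3% coverage at the plan's own rate, 85.7% on average over 0.60 to 0.80, and zero width at 0/15 and 15/15. Because no reporting method is named, the second part of the point is an omission to close and not a wrong analysis already chosen. The issue is worth correcting, but it does not threaten the design.

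**What to change.** Make two changes in the statistical section.

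1. Name one small-sample method, Clopper-Pearson or Wilson, for all reported 90% CIs for proportions, covering the ablation categories and any SAE proportions, and including counts of 0 and 15.
2. Replace the precision sentence with a full width on the same basis. With 15 patients and a true rate of 70%, the expected full width is about 0.41 (maximum 0.456) for Clopper-Pearson, or about 0.35 (maximum 0.390) for Wilson. If the Wald figure is kept for reference, label it as half-width 0.195, full width 0.39, at 70%.

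Clopper-Pearson suits a preference for guaranteed coverage, at the price of wider intervals. Wilson suits a preference for coverage near 90% on average, accepting dips at some rates.

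The cost is two sentences. The stated precision will look less favourable than 0.195, but under Wilson that comes entirely from correcting the label: its expected width of 0.351 is below the true Wald width of 0.389. Sample size, conduct and the toxicity stopping rule do not change.

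### Does the plan need a table of ablation result by laser power, with numbers treated, to match its SAE counts by laser power?

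*Combined protocol and SAP*

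**What the plan says.** The descriptive paragraph of Statistical Considerations and Sample Size Justification opens with a general undertaking: "We will calculate the appropriate summary statistics and 90% confidence intervals (CIs) for the measures of interest described in primary and secondary objectives". Two illustrations follow. For the ablation outcome, "we will obtain frequencies and proportions of the three tumor ablation outcome categories (complete, quasi-complete, and incomplete) for the primary objective". For safety, the analysts will "record the number of each type of SAE at each level of laser power". The second is the only mention of power level in the readable text. The stated aim is to "obtain preliminary estimates of this technique to proceed to our next project", a randomized comparison with SBRT.

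The Sample Size Justification treats the ablation outcome as a single rate: "A total of 15 patients will be recruited from UT MD Anderson Cancer Center", and "the 90% confidence interval for an expected 70% of complete ablation rate can be estimated with a maximum width of 0.195". Toxicity Monitoring likewise works with one quantity, "the true proportion of patients who experience unacceptable toxicities", with no index for power. The only rule on the analysis set is that it contains the patients who actually had an ablation.

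**The concern.** Counting SAEs by power level implies that power is expected to differ between treatments and that the difference may matter. Three consequences would then follow.

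- A count of SAEs at a level is not a rate until the number treated at that level is known.
- The overall complete-ablation rate becomes an average over the levels used, weighted by how many patients received each.
- Harm would be reported by setting and benefit would not, so the two could not be weighed at the same setting when the next trial is designed.

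For a pilot whose purpose is to inform a later trial, that would be a real loss, and one cross-tabulation would appear to cure it.

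**Working it through.** **Inputs.** 15 patients and an expected complete-ablation rate of 70% (Sample Size Justification); 90% intervals (descriptive paragraph), so z = 1.645 two-sided. The number of power levels and the patients at each are not in the readable text; every split below is an assumption.

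**1. The plan's own figure.** Half-width = 1.645 × √(0.70 × 0.30 / 15) = 1.645 × √0.014 = 0.1946, which rounds to the stated 0.195. It is a half-width; the full width is 2 × 0.1946 = 0.389. It needs all 15 patients in one group, so the planned ablation estimate is a pooled rate.

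**2. Precision by level, equal split assumed.** Half-width = 1.645 × √(0.21 / n):

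| Levels | Patients per level | 90% half-width at 70% |
|---|---|---|
| 1 | 15 | 0.195 |
| 2 | 7.5 | 0.275 |
| 3 | 5 | 0.337 |
| 4 | 3.75 | 0.389 |
| 5 | 3 | 0.435 |

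An observed 4 of 5 has a 90% interval of 0.343 to 0.990 (exact) or 0.435 to 0.954 (Wilson). Rates by level would be compatible with almost any ordering of the levels.

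**3. What missing denominators would do.** Two SAEs are 2/3 = 67% (exact 90% interval 0.14 to 0.98), 2/5 = 40% (0.08 to 0.81) or 2/10 = 20% (0.04 to 0.51). The denominator plainly matters. But safety is a secondary objective, and the general undertaking promises 90% intervals for it. An interval for a proportion cannot be computed without a number treated. The text does not say that this is done per level, but a by-level SAE table would ordinarily carry that column.

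**4. What the mix of levels would do.** Assume true complete-ablation rates of 50%, 70% and 90% at three levels:

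- 5/5/5 patients: (5 × 0.5 + 5 × 0.7 + 5 × 0.9) / 15 = 0.70
- 9/3/3 patients: (9 × 0.5 + 3 × 0.7 + 3 × 0.9) / 15 = 0.62
- 3/3/9 patients: (3 × 0.5 + 3 × 0.7 + 9 × 0.9) / 15 = 0.78

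Even with levels set this far apart, the overall rate moves by 0.08 either way, less than half of the 0.195 sampling half-width (0.08 / 0.195 = 0.41). The pooled figure remains a correct summary of these patients as treated.

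**5. The passages side by side.** The ablation rate is pooled, the toxicity proportion is pooled, and the SAE counts are additionally listed by power. These fit together: two overall quantities and one descriptive breakdown. No number or rule in one place contradicts another.

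**The case for a change.** The best case for a change is that it costs almost nothing and protects the primary outcome. The grammar favours a pooled reading: the ablation clause stands on its own, tied to the primary objective, and the power qualifier comes only after a separate verb. Naming the table in advance would prevent a choice made after the results are seen. The noise in by-level figures is no defence either, because the planned SAE counts by power carry the same noise and would hide it if no denominators were shown.

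Part of this stands. The pooled reading is the more natural one, and the table would be useful if power varies between patients. If one patient can be treated at more than one power, some convention for assigning that patient to a level would be needed, and the readable text gives none.

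The rest does not carry. The clauses are examples, so the table is left open. The plan states that it is not powered for comparison, and nothing in the readable text selects a power setting from these data, so there is little for a later choice of table to distort. The SAE breakdown already requires power to be recorded, so the cross-tabulation can be produced afterwards. The readable copy also contains no description of the ablation procedure; the levels and their assignment may be defined there, and their absence from this copy cannot be held against the plan.

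**Conclusion.** No change to the plan follows. The observation is accurate: in the readable text only the SAE counts carry a power level, and no number treated per level is named. But this is table-layout detail that analysts fill sensibly, within an undertaking already wide enough to cover it. Followed as written, the plan yields a sound pooled ablation estimate with a 90% half-width of 0.195 at a 70% rate, and its toxicity rule is unaffected.

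The by-level figures would be very imprecise: about 0.34 either side with 5 patients at a level, if there are three equal levels. The size of any effect of the level mix rests wholly on assumed rates and allocations. When the results are tabulated, showing for each power level the number treated, the ablation categories and the SAEs, all labelled descriptive, would be good practice and needs no amendment.

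### The 0.195 given as the width of the 90% CI is its half-width; with 15 patients and a 70% rate the full width is about 0.39

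*Combined protocol and SAP*

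**What the plan says.** Under Statistical Considerations and Sample Size Justification, the paragraph headed Sample Size Justification fixes enrolment: "A total of 15 patients will be recruited from UT MD Anderson Cancer Center". It then gives one numerical reason for that number: "the 90% confidence interval for an expected 70% of complete ablation rate can be estimated with a maximum width of 0.195". The next sentence gives the source: "This power was based on nQuery Advisor". No formula or interval method is named.

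The same paragraph says that the trial "is not powered for significance in statistical comparison as there is insufficient existing evidence to predict the likely outcomes". The analysis text earlier in the section says "We will calculate the appropriate summary statistics and 90% confidence intervals (CIs) for the measures of interest", and gives the aim as to "assess the magnitude and obtain preliminary estimates of this technique to proceed to our next project", that project being a randomized comparison with SBRT. Only patients who undergo the ablation are to be analysed.

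**The concern.** The width of a confidence interval is the distance between its two limits. Read that way, 0.195 promises that the complete ablation rate will be located within a band of about 20 percentage points. That is implausibly tight for 15 patients at a rate near 70%. The text nowhere says half-width, margin of error, or plus or minus.

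The trial tests no hypothesis, so the precision of its estimates is what the sample size buys. Anyone judging before the start whether 15 patients can inform the assumptions of a later randomized trial would rely on this sentence, and would believe the estimate to be twice as precise as it will be.

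**Working it through.** **Inputs.** From Sample Size Justification: n = 15, expected complete ablation rate p = 0.70, 90% confidence, stated width 0.195. Assumed, because the plan does not say: a two-sided interval, so z = 1.645.

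**Step 1: reproduce the stated figure.** The normal-approximation (Wald) half-width is

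z × √(p(1 − p)/n) = 1.645 × √(0.70 × 0.30 / 15) = 0.1946,

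which rounds to 0.195. Solving back for a half-width of 0.195 gives n = 0.21 × (1.645/0.195)² = 14.94, that is, 15. So the number reproduces as the distance from the estimate to one limit. The one-sided 90% distance, 0.152, does not match.

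**Step 2: the full width on the same basis.** 2 × 0.1946 = 0.389, running from 0.505 to 0.895.

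**Step 3: could another method give a full width of 0.195?** A rate of exactly 70% is not attainable with 15 patients; the nearest results are 10/15 and 11/15.

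| Two-sided 90% method | Full width at 10/15 | Full width at 11/15 |
|---|---|---|
| Wald | 0.400 | 0.376 |
| Wilson | 0.372 | 0.353 |
| Jeffreys | 0.379 | 0.357 |
| Clopper-Pearson (exact) | 0.436 (42.3% to 85.8%) | 0.414 (48.9% to 90.3%) |

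At p = 0.70 itself, Wilson gives 0.363, Agresti-Coull 0.368 and Wald with continuity correction 0.456. None comes near 0.195.

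**Step 4: when would so narrow an interval be seen?** With Wilson or exact limits, a full width of 0.195 or less occurs only at 0/15 or 15/15 (Wilson 0.153, exact 0.181); at 1/15 and 14/15 the widths are already 0.236 and 0.276. If the true rate is 70%, the chance of 15/15 is 0.7¹⁵ = 0.0047, about 0.5%, and 0/15 is negligible. The same holds for Wald limits left untruncated. If Wald limits are cut at 0 and 1, then 1/15 and 14/15 also qualify (14/15: 0.827 to 1, width 0.173), and the chance rises to about 3.5%.

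**Step 5: sample size for a true full width of 0.195 at 70%.** n = 0.21 × (2 × 1.645/0.195)² = 59.8, about 60 by the normal approximation. The exact width first falls below 0.195 at 68 patients (48/68: 0.194).

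**Step 6: the word *maximum*.** The Wald half-width is largest at p = 0.50: 1.645 × √(0.25/15) = 0.212, full width 0.425. The largest exact full width for any result out of 15 is 0.456. So 0.195 is not an upper bound over possible results, even as a half-width. If fewer than 15 are ablated, the interval widens further: with 12 analysed, the half-width at 70% is 1.645 × √(0.21/12) = 0.218.

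**The case against.** The strongest reply concerns weight. This is a descriptive pilot. No success threshold, go/no-go rule or test uses 0.195, and the reported intervals will be computed from the data, so the mislabel will not carry into the results or into the planning of the next trial. Since 15 patients do give a half-width of 0.195, the sample size is not shown to be wrong. All of that stands and limits the seriousness of the point. It does not make the sentence correct.

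Three narrower objections also have force:

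- The plan gives no formula. That the normal approximation was used is an inference from its reproducing 0.195; it is a strong inference, but not a statement in the document.
- The figure is tied to an expected rate of 70%, so *maximum* need not mean the largest width over all rates. That remark is minor, as is the use of *power* for a precision.
- The plan recruits 15 but analyses only those ablated, and some recruited patients may prove ineligible at bronchoscopy. It does not say whether they count toward the 15, so any restated precision should be conditional on all 15 being analysed.

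**Conclusion.** The statement is wrong as written. The 0.195 is a half-width; the full width at 70% with 15 patients is about 0.39 by the normal approximation, and 0.35 to 0.44 at 10/15 and 11/15 across the four methods tabulated. Stated precision is overstated by a factor of two (0.389/0.195 = 2.0). The conclusion assumes a two-sided interval and 15 analysed patients; fewer would widen it. It does not depend on which of the standard methods is used.

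The point should be fixed because this is the only numerical support for the sample size in a trial meant to produce estimates. It is not grounds for changing enrolment, the endpoint or the toxicity monitoring.

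**What to change.** Replace the precision sentence with wording such as:

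> If all 15 patients are analysed and the complete ablation rate is 70%, the two-sided 90% confidence interval extends about 0.195 either side of the estimate (full width about 0.39, normal approximation). Exact 90% intervals would be 42.3% to 85.8% for 10/15 and 48.9% to 90.3% for 11/15; the largest exact full width for any result is 0.46.

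Drop *maximum* from the 0.195 figure, and in the following sentence change *power* to *precision*.

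The cost is one or two sentences and a less favourable stated precision, with no extra patients or procedures. Naming the method for the reported 90% intervals in the same edit would be useful, but it is optional and separate from this error.
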